#### 2.5.4. **Exploratory Variables**

The exploratory variables planned in the protocol, will not be analyzed due to the early study termination and the low number of subjects randomized.

Sponsor:	ObsEva		
Protocol:	19-OBE2109-00	5	
Document Version No.:	1.0	Document Date:	18-MAY-2021

## 3. SUBJECT POPULATIONS

### 3.1. Analyses Sets Definitions

The following data sets will be used for the statistical analysis:

Extension Safety Analysis Set: All subjects randomized who entered the extension study and received at least one dose of study drug in the extension study irrespective of the treatment received. Subjects will be analyzed according to treatment received

Follow-up Extension Safety Analysis Set: All subjects randomized who entered the extension study and who entered the drug free extension follow-up period. Subjects will be analyzed according to treatment received.

The actual treatment for the extension study will be derived as follows, based on daily e-diary IMP intake data:

Subjects received a different kit of active linzagolix for each month, and a different kit for add-back or placebo for each 3-month period.

The number of days with one pink tablet, one grey tablet and one red capsule taken based on e-diary IMP intake data for each treatment will be computed. Data from "Today" will be used primarily. If data from today is missing, data from "Yesterday" of the following day will be considered. If the e-diary is not completed for a day (neither "Today" nor "Yesterday" of following day), it will be assumed that no drug was taken on that day.

Further rules are as follows:

- Treatment administration errors:
  - If a subject received placebo with placebo ABT on more than 50% of days (even if it is not planned), then the actual treatment group will be placebo with placebo ABT for the extension period.
  - Otherwise, the active treatment (combined with add-back or placebo add-back) with the most days taken will be assigned for the extension period.
  - If the number of days is equal for two treatments groups containing active treatment, then LGX 200 mg with ABT will be assigned for the extension period.
- If a subject discontinued, only data received up to discontinuation will be used.

All analyses for the extension study will be described according to the combined treatment group based on the treatment on the main study and the extension study.

Sponsor:	ObsEva		
Protocol:	19-OBE2109-00	5	
Document Version No.:	1.0	Document Date:	18-MAY-2021

For combined planned treatment groups, the planned treatment during the main study and the planned treatment during the extension study comprise the following four combined planned treatment groups:

- Placebo / LGX 75 mg: for subjects randomized to placebo in the main study and randomized to • LGX 75 mg in the extension study
- Placebo / LGX 200 mg + ABT: for subjects randomized to placebo in the main study and • randomized to LGX 200 mg + ABT in the extension study
- LGX 75 mg: for subjects randomized to LGX 75 mg in the main study and continued with the same • treatment in the extension study
- LGX 200 mg + ABT: for subjects randomized to LGX 200 mg + ABT in the main study and continued • with the same treatment in the extension study

For the combined actual treatment groups, the actual treatment during the main study and the actual treatment during the extension study comprise the following four combined actual treatment groups. It is possible that the derived actual treatment group will not correspond to any of the combined planned treatment groups; thus the combined actual treatment group will be derived as follows:

Actual treatment Main study	Actual treatment Extension study	Combined actual treatment group				
Combination planned in the protocol						
Placebo	LGX 75 mg	Placebo / LGX 75 mg				
Placebo	LGX 200 mg + ABT	Placebo / LGX 200 mg + ABT				
LGX 75 mg	LGX 75 mg	LGX 75 mg				
LGX 200 mg + ABT	LGX 200 mg + ABT	LGX 200 mg + ABT				
Combination not planned in the p	protocol (but possible with treatmen	nt administration errors)				
Placebo	Placebo	Placebo / LGX 75 mg				
LGX 75 mg	Placebo	LGX 75 mg				
LGX 200 mg + ABT	Placebo	LGX 200 mg + ABT				

CRS-BS-TP-000005 V 1.0

#### Page 23 of 66

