### 2.2. Randomization Methodology

Subjects who previously received placebo were randomized in a 1:1 ratio to either linzagolix 75 mg alone (with ABT placebo) or linzagolix 200 mg with ABT), as per the main study randomization schedule. Subjects were randomized into permutated blocks of a pre-determined length.

Subjects who received active treatment continued with the same treatment (linzagolix 75 mg alone or linzagolix 200 mg with ABT).

In order to maintain the blind, the sites were not required to perform any randomization activities. The kits were automatically allocated to the corresponding patients in the IWRS upon confirmation of their eligibility.

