## 4.2. General Statistical Methods and Data Handling

## 4.2.1. General Methods

All output will be incorporated into Microsoft Excel or Word files, sorted and labeled according to the International Conference on Harmonisation (ICH) recommendations, and formatted to the appropriate page size(s).

Tabulations will be produced for appropriate demographic, baseline, and safety parameters.

The analyses will be performed on 4 treatment groups (taking into account the treatment taken in the main study):

- linzagolix 75 mg / linzagolix 75 mg
- linzagolix 200 mg with ABT / linzagolix 200 mg with ABT
- Placebo / linzagolix 75 mg (subject receiving placebo in main study and treated with linzagolix 75 mg in extension study)
- Placebo / linzagolix 200 mg with ABT (subject receiving placebo in main study and treated with linzagolix 200 mg with ABT in extension study)

For continuous data and for ordered categorical data, if appropriate, the number of non-missing observations, mean, standard deviation, median, first and third quartiles, minimum and maximum will be calculated, including for change from baseline when applicable. The baseline mean will be calculated for all subjects based on the Safety Set. For Bone Mineral Density, a baseline mean will also be calculated for each visit using the baseline data for the subset of subjects who attended that visit, such that the same subjects contribute to the mean for the visit and the mean for the corresponding baseline values.

Sponsor:	ObsEva		
Protocol:	19-OBE2109-005		
Document Version No.:	1.0	Document Date:	18-MAY-2021

Summary statistics will be based primarily on non-missing values. For ordered categorical data and nominal data, absolute counts and relative frequencies (in %) will be calculated.

Raw and derived data will be listed.

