#### 4.2.11. Baseline Definitions

The baseline will be described in two ways:

- Main Baseline, defined in the Statistical Analysis Plan of the main study and calculated according to first dose of IMP taken during the main Study.
- Second Baseline (named Baseline 2), defined as the last assessment before the first active dose of IMP during the extension study. The baseline 2 will be calculated only for the subjects who are in the placebo arm (actual arm) in the main study.

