## 4.8.3. Bone Mineral Density (BMD) by DXA

BMD of femoral neck, total hip and lumbar spine will be assessed by DXA at Baseline, Month 9 (if required) Month 12 and Month 6 of the extension follow-up (if required). Unacceptable DXA assessments (accepted="No") will not be summarized (hip, spine and femur considered separately).

In case of repeated values due to BMD loss ≥5%, the initial scan will be used in summaries. Initial and repeated scan values will be reported in the listings.

Calibrated values will be used if available, otherwise initial values will be considered.

BMD, expressed as both absolute values and Z-scores will be summarized at each visit in terms of actual values, changes from baseline, changes from baseline 2 (only for the subjects who are in the placebo arm in the main study) for each anatomic location. For absolute values only, percent change from baseline, percent changes from baseline 2 (only for the subjects who are in the placebo arm in the main study) and 95% confidence interval for the mean percent change from baseline and for the mean percent change from baseline 2 within each group will be produced at each time point.

The definition of both baselines are described in section 4.2.11.

Percent change from baseline and percent change from baseline 2 to Month 9, Month 12 and Month 6 extension follow-up will be described and will also be summarized in categories of percentage with the following classes:

- No change or increase,
- Decrease ≤ 3%,
- Decrease > 3% and  $\leq 5\%$ ,
- Decrease > 5% and  $\leq$  7%,
- Decrease > 7% and  $\leq$  8%,
- Decrease > 8%.

All data will be listed.

CRS-BS-TP-000005 V 1.0

Sponsor:	ObsEva		
Protocol:	19-OBE2109-00	5	
Document Version No.:	1.0	Document Date:	18-MAY-2021

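### SAP 3.1 counts a woman derived as placebo in both studies as Placebo / LGX 75 mg, although the safety sets go by treatment actually taken

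*SAP*

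**What the plan says.** For both the Extension Safety Analysis Set and the follow-up safety set, SAP section 3.1 states: "Subjects will be analyzed according to treatment received". Protocol section 13.4 takes the same line for the Extension Safety Analysis Set.

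Section 3.1 then derives the extension treatment from daily diary intake. Under its sub-heading on administration errors, if placebo with placebo add-back was taken on more than 50% of days, "then the actual treatment group will be placebo with placebo ABT for the extension period". Otherwise the active treatment with the most days is assigned.

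The SAP recognises that a derived pair of treatments may match no planned group, and introduces its table with "thus the combined actual treatment group will be derived as follows". The row for placebo in the main study and placebo in the extension gives the group Placebo / LGX 75 mg.

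Section 4.2.1 defines that group for the tables: "Placebo / linzagolix 75 mg (subject receiving placebo in main study and treated with linzagolix 75 mg in extension study". All extension analyses are to be presented by combined group.

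**The concern.** Three statements cannot all be true of one woman: she is analysed by what she took, what she took is placebo, and her group is the one treated with 75 mg in the extension.

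At stake is the accuracy of the safety tables for former-placebo women. Such a woman's adverse events, laboratory values and bone mineral density change from main-study baseline would be reported as those of a woman who switched to 75 mg. Her person-time without active treatment would sit in a group read as active exposure. In a group expected to be small, one woman can shift a percentage visibly.

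**Working it through.** **Step 1. List the pairs.** There are three possible derived treatments in each study, so 3 × 3 = 9 pairs, of which 4 are planned and 9 − 4 = 5 are not. The groups below come from the table in SAP 3.1.

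| Main study (derived) | Extension (derived) | Group assigned | Is the active drug in the label a derived treatment? |
|---|---|---|---|
| Placebo | 75 mg | Placebo / LGX 75 mg | Yes, extension |
| Placebo | 200 mg + ABT | Placebo / LGX 200 mg + ABT | Yes, extension |
| 75 mg | 75 mg | LGX 75 mg | Yes, both |
| 200 mg + ABT | 200 mg + ABT | LGX 200 mg + ABT | Yes, both |
| Placebo | Placebo | Placebo / LGX 75 mg | **No, in neither study** |
| 75 mg | Placebo | LGX 75 mg | Yes, main |
| 200 mg + ABT | Placebo | LGX 200 mg + ABT | Yes, main |
| 75 mg | 200 mg + ABT | LGX 75 mg | Yes, main |
| 200 mg + ABT | 75 mg | LGX 200 mg + ABT | Yes, main |

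In all five unplanned rows the label departs from the derived extension treatment. In four of them it keeps the derived main-study treatment. Only the placebo/placebo row names an active drug that is derived in neither period.

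**Step 2. Check that the row can be reached.** Take 6 × 28 = 168 extension days as the denominator. This is an assumption, because the SAP does not say which days the 50% refers to.
- Placebo on 168 of 168 days: 100%, derived as placebo, group Placebo / LGX 75 mg.
- Placebo on 85 of 168 days: 50.6%, derived as placebo, same group.
- Placebo on 84 of 168 days: 50.0%, not more than half, so the placebo rule does not apply.

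The SAP's own rules therefore lead to this row, given an administration error.

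**Step 3. Check whether anything removes her from the tables.** Listing 16.2.3.2 covers women whose actual treatment matches no planned group, so she would be visible there. Under SAP 3.2 a dispensing error is a major deviation and is tabulated by group. Neither step takes her out of Placebo / LGX 75 mg.

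**Step 4. Weight of one woman.** The planned size reproduces: 450 × 0.80 = 360 completers, and 360 × 0.80 = 288 entering the extension. Assuming equal retention across the three main-study arms, 288 / 3 = 96 former-placebo women. The 1:1 randomisation gives 96 / 2 = 48 per switch group, so one woman is 1/48 = 2.1 percentage points. SAP 1.2 says enrolment was substantially below target but gives no group size. For an assumed group of 20 one woman is 1/20 = 5 points; for 10 it is 1/10 = 10 points.

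**The case against.** The strongest defence is that the row is an open convention: the SAP foresees unplanned pairs, assigns each one in advance, and lists the women concerned. The case should also be rare. Neither extension arm is placebo only (Protocol 11.2), and kits are allocated by the IWRS (Protocol 11.6). If a group must be chosen, 75 mg with placebo add-back is the planned arm closest to placebo with placebo add-back. This stands as a reason to call the point minor. It does not make the label true.

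A reader might infer more than the documents support:

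- **That all five unplanned rows are equally wrong.** The other four are inexact for the extension half, but each label names a treatment derived for the main study. They need at most a footnote.
- **That half of the women in this row would come from the 200 mg + ABT arm**, because "Subjects who previously received placebo were randomized in a 1:1 ratio to either linzagolix 75 mg alone" or 200 mg with ABT. The randomisation ratio is not the ratio of errors. Linzagolix and add-back come in separate kits (Protocol 11.3), and the 75 mg arm already takes placebo add-back. A woman assigned 75 mg reaches the row if only her linzagolix kits are wrong. A woman assigned 200 mg + ABT needs both kit types wrong.
- **That her data would distort the bone density change from Baseline 2.** Baseline 2 is "defined as the last assessment before the first active dose of IMP during the extension study", and a confidence interval "for the mean percent change from baseline 2 within each group will be produced at each time point". If she took active drug on a minority of days, she has a valid Baseline 2. If she took none, the natural reading is that it is missing, and section 4.2.1 bases summaries primarily on non-missing values. She would then drop out of that mean and interval. The SAP should say so.
- **That a woman with no diary intake defaults to 200 mg + ABT through a 0 = 0 tie.** The rule reads: "If the number of days is equal for two treatments groups containing active treatment, then LGX 200 mg with ABT will be assigned". But it sits under administration errors. Under the double-dummy design the diary shows only that units were taken, so treatment identity must come from the kits. A woman dispensed only 75 mg kits has no second active treatment to tie with. This leaves a wording note at most.

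**Conclusion.** The point holds and is minor. One row of the combined-group table gives a label that contradicts both the by-treatment-taken principle in SAP 3.1 and the group definition in SAP 4.2.1.

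Its effect is confined to descriptive safety summaries of the Placebo / LGX 75 mg group; no hypothesis test is planned. The number of women affected is not given and may be zero. The figures of 2.1 points at the planned 48 and 5 to 10 points at an assumed 10 to 20 are weights per affected woman. A reader might take 2.1 as a minimum effect, but the minimum is zero. The planned figure assumes equal retention across the main-study arms, and the smaller group sizes are assumptions, not figures from the documents.

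**What to change.** Change the placebo/placebo row so that these women are shown in a separate row, a footnote or listings only, and are not counted in Placebo / LGX 75 mg. Add a sentence to section 4.2.11 that Baseline 2 is missing when no active extension dose was taken.

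As an optional clarification in section 3.1, say that the tie rule applies only to non-zero day counts, and that dispensed-kit or accountability records decide the treatment when diary intake is absent. Protocol 11.5 already requires kit numbers and accountability to be recorded.

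The cost is one table row or footnote and one to three sentences. No new data are needed.

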# Cytel

## Statistical Analysis Plan

Sponsor:	ObsEva		
Protocol:	19-OBE2109-00	5	
Document Version No.:	1.0	Document Date:	18-MAY-2021

LGX 75 mg	LGX 200 mg + ABT	LGX 75 mg
LGX 200 mg + ABT	LGX 75 mg	LGX 200 mg + ABT

### 3.2. **Protocol Violations**

A protocol deviation is any noncompliance with the clinical trial protocol or International Conference on Harmonization Good Clinical Practice (ICH GCP) requirements. It was the responsibility of the site investigator to use continuous vigilance to identify and report deviations. All deviations were to be addressed in study source documents and reported to the reviewing IRB/REB per their policies. The site investigator was responsible for knowing and adhering to the reviewing IRB/REB requirements.

All Protocol Deviations were to be reported to the Sponsor and documented in the monitoring report. These will be classified as minor or major based on their effect on the right, safety or well-being of the subjects and/or the quality and integrity of the data. The following deviations will be considered as major:

- Non-compliance with inclusion criteria 2
- Non-compliance with exclusion criteria 2; 3; 4; 5; 6
- IP Dispensing error;
- Randomisation code broken

The final rating of all deviations will be confirmed prior the unblinding. The final protocol deviation file (formatted as a Microsoft Excel file) will be provided to Cytel.

Major protocol deviations will be summarized by category and by treatment group on the Extension Safety Analysis Set.

All protocol deviations will be presented in the data listings.

Cytel Confidential: This is a controlled document and shall not be changed, saved, copied or reproduced by any unauthorized person.

Sponsor:	ObsEva		
Protocol:	19-OBE2109-005		
Document Version No.:	1.0	Document Date:	18-MAY-2021

## 4. STATISTICAL METHODS

## 4.1. Sample Size Justification

With a planned sample size of 150 subjects per each of the three treatment groups in the main study (450 subjects in total), the power was to be greater than 95% to reject the null hypothesis for both coprimary endpoints and 85% to reject all the null hypothesis for the ranked secondary endpoints. All subjects who completed the full 6-month Treatment Period in the main study and who met the inclusion criteria were to be offered to enter the extension study. It was estimated that up to 288 subjects would enter the extension study, assuming that 80% of the patients randomized in the main study would complete the study (~ 360 subjects) and that up to 80% thereof would enter the extension study.

## 4.2. General Statistical Methods and Data Handling

## 4.2.1. General Methods

All output will be incorporated into Microsoft Excel or Word files, sorted and labeled according to the International Conference on Harmonisation (ICH) recommendations, and formatted to the appropriate page size(s).

Tabulations will be produced for appropriate demographic, baseline, and safety parameters.

The analyses will be performed on 4 treatment groups (taking into account the treatment taken in the main study):

- linzagolix 75 mg / linzagolix 75 mg
- linzagolix 200 mg with ABT / linzagolix 200 mg with ABT
- Placebo / linzagolix 75 mg (subject receiving placebo in main study and treated with linzagolix 75 mg in extension study)
- Placebo / linzagolix 200 mg with ABT (subject receiving placebo in main study and treated with linzagolix 200 mg with ABT in extension study)

For continuous data and for ordered categorical data, if appropriate, the number of non-missing observations, mean, standard deviation, median, first and third quartiles, minimum and maximum will be calculated, including for change from baseline when applicable. The baseline mean will be calculated for all subjects based on the Safety Set. For Bone Mineral Density, a baseline mean will also be calculated for each visit using the baseline data for the subset of subjects who attended that visit, such that the same subjects contribute to the mean for the visit and the mean for the corresponding baseline values.

Sponsor:	ObsEva		
Protocol:	19-OBE2109-005		
Document Version No.:	1.0	Document Date:	18-MAY-2021

Summary statistics will be based primarily on non-missing values. For ordered categorical data and nominal data, absolute counts and relative frequencies (in %) will be calculated.

Raw and derived data will be listed.

### 4.2.2. **Computing Environment**

All descriptive statistical analyses will be performed using SAS statistical software (Version 9.4), unless otherwise noted. Medical History and adverse events will be coded MedDRA version 23.0. Concomitant medications will be coded using World Health Organization (WHO) Drug Dictionary B3 – Mar 2019.

### 4.2.3. Methods of Pooling Data

Not applicable to the present study.

### 4.2.4. Adjustments for Covariates

Not Applicable

## 4.2.5. Multiple Comparisons/Multiplicity

No formal hypothesis tests are planned for this extension study. Data will be summarized by timepoint for each treatment group.

#### 4.2.6. **Subpopulations**

Not Applicable.

## 4.2.7. Withdrawals, Dropouts, Loss to Follow-up

In general, there will be no substitutions made to accommodate missing data points due to withdrawals, dropouts and loss to follow-up. All data recorded in the CRF will be included in data listings that will accompany the clinical study report.

In case of early discontinuation, the subject was to be instructed to complete the relevant eDiary questionnaires as soon as possible upon treatment discontinuation.

Sponsor:	ObsEva		
Protocol:	19-OBE2109-005		
Document Version No.:	1.0	Document Date:	18-MAY-2021

## Withdrawal during treatment period:

Subjects discontinuing participation in the study during the Treatment Period were to undergo the procedures required at Month 12, except the DXA in case of discontinuation before Month 9 visit. These subjects were to enter the 6-month Follow-Up Period and were to continue daily eDiary recording for 6 months and up to the Month 6 ExFU visit in order to continue to collect efficacy and safety data.

PK sampling was not required if the subject had no IMP administration the day prior to the withdrawal visit.

## Withdrawal during follow-up period:

Subjects discontinuing participation in the study during the Follow-Up Period were to undergo the procedures required at the Month 6 ExFU visit, which included completion of all ClinRO and ePRO questionnaires, except for DXA scans in subjects who discontinued before the Month 3 ExFU visit.

### 4.2.8. Missing, Unused, and Spurious Data

#### 4.2.8.1. Adverse events and Concomitant Medication Missing Dates

Imputation of missing/partial AE and CM dates will be done only to identify treatment-emergent AEs.

#### AE onset dates:

- Partially missing AE onset dates will be imputed as follows:
  - When only Day is missing:
    - If Month & Year of the onset date are the same as Month & Year of the first administration date, the imputed onset date will be imputed as the minimum of the first administration date and the AE resolution date (imputed if needed).
    - Else if the subject entered the Extension Study and Month & Year is the same as Month & Year of the first administration date in Extension, the imputed onset date will be imputed as the minimum of the first administration date in Extension and the AE resolution date (imputed if needed).
    - Otherwise, the missing day will be replaced by "1"
  - When Day & Month are missing:
    - If the subject entered the Extension Study and if Year of the onset date is the same as Year of the first administration date in Extension, the imputed onset

Sponsor:	ObsEva		
Protocol:	19-OBE2109-005		
Document Version No.:	1.0	Document Date:	18-MAY-2021

date will be imputed as the minimum of the first administration date in Extension and the AE end date (imputed if needed).

- Else if Year of the onset date is the same as Year of the first administration date, the imputed onset date will be imputed as the minimum of the first administration date and the AE end date (imputed if needed).
- Otherwise, the missing Day & Month will be replaced by "01 JAN."
- Completely missing AE onset dates will be imputed as follows:
  - If the subject entered the Extension, the AE onset date will be imputed by the first administration date in Extension and the AE will be considered as treatment-emergent, unless the end date of the AE (imputed if needed) or the end year of the AE (if day and month are missing) is entered and is before the first administration date in Extension.
  - If the subject did not enter the Extension, or if the end of the AE is before the first administration date in Extension, the AE onset date will be imputed by the first administration date and the AE will be considered as treatment-emergent, unless the end date of the AE (imputed if needed) or the end year of the AE (if day and month are missing) is entered and is before the first administration date. If the end date is before the first administration date, the AE will not be considered as treatment-emergent.

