Median Z scores, interquartile ranges and total ranges for femoral neck, total hip and lumbar spine at baseline, Week 24 and Week 52 did not change importantly over time: medians remained within the range of -0.20 to 0.30, 0 to 0.40, and -0.25 to 0.35 in all treatment groups for the femoral neck, total hip and lumbar spine, respectively. Median absolute change from baseline to Week 52 ranged from -0.10 to 0.00, -0.10 to 0.00 and -0.20 to -0.10, respectively.

Over the 52-week treatment period, 154/176 (87.5%) of subjects reported treatment emergent adverse events (TEAEs). The incidence of TEAEs was not dose-dependent across treatment groups, ranging from 81.8% in the 100 mg group to 93.3% in the 200/100 mg group. The majority of the TEAEs (616/846; 72.8%) were reported during the first 24 weeks of treatment.

The most commonly reported TEAEs were headache (32.4%) and hot flush (28.4%). The majority of these events occurred during the first 24 weeks of treatment. Headaches were reported with a similar frequency across treatment groups, ranging from 22.2% in the 75 mg FD group to 44.8% in the placebo/100 mg group, with no apparent dose relationship. Conversely, the incidence of hot flushes was dose-dependent and increased with increasing exposure to linzagolix: 16.7% (50 mg), 20.7% (75 mg FD), 22.2% (75 mg TD), 24.1% (placebo/100 mg), 27.3% (100 mg), and 60.0% (200/100 mg). Of note, there was no worsening in the incidence of hot flushes during the treatment extension; only 2/61 hot flush events were reported.

19-OBE2109-005 PROTOCOL V2.0 DATED 24 AUGUST 2020

Ten serious AEs (SAEs) were reported in nine subjects. None of the SAEs were considered as related to study treatment. The SAEs of ruptured ectopic pregnancy (50 mg), pelvic pain (50 mg), pneumonia (75 mg TD), and anxiety disorder (200/100 mg) led to subject withdrawal from treatment during the extension phase of the study.

During treatment extension, 12 subjects (6.8%) reported 17 TEAEs leading to treatment withdrawal. In the 200/100 mg group, one subject discontinued treatment due to bone loss and one subject due to bone pain. In the 75 mg FD group, one subject discontinued treatment due to bone density decreased.

There were no subjects with AST and/or ALT values >2×ULN during the treatment extension.

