## AE end dates

- If Day only is missing, incomplete end dates will be replaced by the last day of the month, if not resulting in a date later than the date of the subject's death or date of study discontinuation. In the latter case, the date of death/date of study discontinuation will be used to impute the incomplete end date.
- If Day & Month are missing, Day & Month will be replaced by 31DEC, if not resulting in a date later than the date of the subject's death or date of study discontinuation. In the latter case, the date of death/ date of study discontinuation will be used to impute the incomplete end date.
- In all other cases the incomplete end date will not be imputed.

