### 4.8.2. Adverse Events

Adverse events will be coded using the Medical Dictionary for Regulatory Activities (MedDRA) and displayed in tables and listings using System/Organ/Class (SOC) and Preferred Term.

Analyses of adverse events will be performed for those events that are considered treatment emergent (TEAEs), where treatment emergent is defined as AEs with a start date on or after the first dose of extension study drug through 30 days after discontinuation of study drug or Month 12 visit date, or any event that was present at Month 6 but worsened in intensity or was subsequently considered drug-related by the investigator through the end of the extension study.

Adverse Event tables will be presented for the following periods: Month 6 to Month 12 (Extension treatment period) and Month 12 to Month 6 ExFU (Extension follow-up period) as defined in section 4.2.12.

Adverse events starting more than 30 days after end of treatment will be considered as post-treatment AE.

For each of these 2 study periods, an overall summary table will be prepared presenting, by treatment group, the number and percentage of subjects with

- any AE,
- any TEAE,
- any post-treatment AE (displayed only for the Extension follow-up period),
- Severe TEAE,
- any TEAE assessed by the Investigator as related to Linzagolix ((definite, probable, or possible relationship),
- any TEAE assessed by the Investigator as related to add-back therapy ((definite, probable, or possible relationship),
- any TEAE leading to permanent discontinuation of IMP,
- any serious adverse event (SAE),
- any serious treatment emergent adverse event (Serious TEAE),
- any serious treatment emergent adverse event (SAE) related to Linzagolix,
- any serious treatment emergent adverse event (SAE) related to add-back therapy,
- any fatal TEAE (where outcome is "Fatal")

CRS-BS-TP-000005 V 1.0

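### Adverse events with a missing or year-only onset are dated to the first extension dose without regard to when they were first reported, so some placebo-phase events can be counted as linzagolix TEAEs

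*SAP*

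**What the plan says.** SAP 4.2.8.1 limits the purpose of the imputation: "Imputation of missing/partial AE and CM dates will be done only to identify treatment-emergent AEs".

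- **Completely missing onset, extension entered.** "the AE onset date will be imputed by the first administration date in Extension and the AE will be considered as treatment-emergent". The exception applies when the end date (imputed if needed), or the end year if that is all there is, "is entered and is before the first administration date in Extension".
- **Year-only onset.** The extension is checked first: "if Year of the onset date is the same as Year of the first administration date in Extension", the onset becomes the earlier of the first extension dose and the event's end date. The main-study dose year is consulted only if that check fails.
- **End dates.** "If Day & Month are missing, Day & Month will be replaced by 31DEC", capped at death or study discontinuation. A missing day becomes the last day of the month.

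SAP 4.8.2 then defines an extension TEAE in two limbs. The date limb covers "AEs with a start date on or after the first dose of extension study drug through 30 days after discontinuation of study drug" (or the Month 12 visit). The second limb admits an event already there at Month 6 only if its intensity increased or the investigator later attributed it to the drug.

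**The concern.** The onset rules use onset, end, dose and death or discontinuation dates. None uses the visit, study or eCRF date under which the event was first reported. Main-study events are in scope, because the same rules also provide for women who never entered the extension, and Protocol 12.5 requires ongoing events to be updated through follow-up.

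An event written down during the main study can therefore receive an onset after the date on which it was reported, which is impossible. It then meets the date limb of the TEAE definition, and the second limb, written for events already present at Month 6, is never applied to it.

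This matters most in the two groups that switched from placebo, where the flag changes the treatment to which the event is attributed. Efficacy and PK analyses have been dropped (SAP 4.6, 4.7), so the safety tables are now the main output.

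**Working it through.** The plan gives no figure on this point, so there is none to reproduce. The check applies the rules to test cases.

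**Inputs.** The first extension dose is at Month 6, Day 169 (SAP Table 3), which is 169 − 1 = 168 days after Day 1. The calendar dates are assumed: Day 1 on 3 Feb 2020, first extension dose on 20 Jul 2020 (3 Feb + 168 days), study discontinuation on 20 Dec 2020. Every event below is taken to have been reported during the placebo phase.

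| Onset recorded | End recorded | End date used | Imputed onset | Extension TEAE by date limb |
|---|---|---|---|---|
| missing | none / ongoing | none | 20 Jul 2020 | yes |
| missing | 2020 only | 20 Dec 2020 (31 Dec, capped) | 20 Jul 2020 | yes |
| missing | Jul 2020 | 31 Jul 2020 | 20 Jul 2020 | yes |
| 2020 only | none / ongoing | none | 20 Jul 2020 | yes |
| 2020 only | 2020 only | 20 Dec 2020 (31 Dec, capped) | 20 Jul 2020 | yes |
| 2020 only | 1 Sep 2020 | 1 Sep 2020 | 20 Jul 2020 | yes |
| missing | 10 Apr 2020 | 10 Apr 2020 | 3 Feb 2020 | no |
| 2020 only | 10 Apr 2020 | 10 Apr 2020 | 10 Apr 2020 | no |
| 2019 only | none / ongoing | none | 1 Jan 2019 | no |

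Six case types are moved and three are not. In the second and fifth rows the event may have resolved on placebo and is still moved, because the end-date imputation pushes its end past the dose.

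**Size of the impossible gap.** With 28-day months, a Month 2 visit is Day 57. An undated, ongoing event recorded there gets an onset 169 − 57 = 112 days after its report.

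**How often the year match can apply (year-only records only).** Assume first extension doses spread evenly over a 366-day year. The whole 168-day main-study phase lies in the dose year for (366 − 168)/366 = 198/366 = 54% of dose dates. For a dose i days into the year, the share of the phase in that year is min(i, 168)/168. Its sum over i = 0 to 167 is (167 × 168/2)/168 = 83.5, and the other 198 dates contribute 1 each, so the mean is (83.5 + 198)/366 = 77%. The range is 0% to 100%.

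**Weight of one record.** The planned maximum of 288 entrants over three equal main-study arms is 96 per arm. Halving the placebo arm gives 48 per switch group, assuming equal completion and uptake across arms. One extra woman with an event is then 1/48 = 2.1 percentage points. SAP 1.2 says enrolment was substantially lower without giving the number. At an assumed 20 or 10 women per group, one record is 5 or 10 points.

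**The case against.** The best defence is that counting doubtful events as treatment-emergent is a common convention that errs towards over-reporting, and that few records will be affected. Protocol 12.2.3 asks for onset and resolution dates on every AE report, events are elicited at each visit (12.2.1), and lock waits for data clarifications (14.3). All events are also listed by subject, and nothing is tested. This stands as an argument about size. It does not justify overriding recorded evidence that the event preceded the dose, and the SAP itself gives no rationale for the rule, conservative or otherwise.

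Four stronger readings are tempting, and the documents do not support them:

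- **Every undated main-study event is moved.** It is not: a full end date before the first extension dose keeps it out, and a year-only onset moves only when the year matches.
- **Most affected records are misplaced.** Protocol 5.5.3 reports for the Phase 2b extension cohort: "The majority of the TEAEs (616/846; 72.8%) were reported during the first 24 weeks of treatment". That share covers all TEAEs in another trial over the treatment period only. It ignores the end-date condition, which already removes many early events, so it is not an error rate for this rule.
- **The events disappear from the main-study tables.** The main study has its own SAP, which is not among these documents, and this SAP tabulates only extension periods.
- **The two partial-date rules check the doses in inconsistent order.** When only the day is missing the order cannot matter, because doses 168 days apart never share a month. In the year-only rule it does matter, but checking the main study first would move true extension onsets the other way.

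**Conclusion.** The point holds as a limited defect. The stated rule can assign an onset later than the event's own report and flag that event as an extension TEAE without the worsening or relatedness that SAP 4.8.2 requires of events present at Month 6. The exposed records are those reported before the first extension dose, with a missing onset or a year-only onset in the dose year, and with no entered end date that places resolution before that dose.

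A change of attributed treatment, from placebo to linzagolix, arises only in the two Placebo / LGX groups. In the continued-active groups the event moves between periods on the same drug.

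The number of records cannot be derived from the documents and is probably small. The 54% and 77% rest on evenly spread dose dates and describe only how often the year match could apply. They do not estimate how many events are misclassified. The change is still worth making, because safety is now the main output and single records carry weight in small groups.

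**What to change.** Add to SAP 4.2.8.1 that an imputed onset may not be later than the date or visit at which the event was first recorded. Where no recording date is available, use the study or visit under which it was reported. If that precedes the first extension dose, treat the event as present at Month 6, so that it is an extension TEAE only through the worsened or drug-related limb of SAP 4.8.2. That limb must be kept explicitly, or valid TEAEs would be lost. Under Protocol 10.1 the Month 6 assessments come before that day's dose, so the text should also say how events first recorded at that visit are handled.

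The wording costs a sentence or two. The real cost is bringing the recording visit or date into the AE dataset. Neither document confirms that it is available there, and the list of AE report contents in Protocol 12.2.3 does not include it. Slightly fewer undated events will be counted as extension TEAEs. The main and extension studies are locked together (SAP 2.3.2), so the report's study of origin should be identifiable even if the exact date is not.
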